## **XII. Data Safety Monitoring Plan**

Patient confidentiality during this study will be protected in compliance with HIPAA (Health Insurance Portability and Accountability) requirements as well as the requirements of the University of Missouri Health Sciences IRB. All subjects will have a de-identified Subject Study ID number. All subject information in electronic format will be kept in password-protected storage. All subject information in paper format will be kept in locked cabinets in a secured suite at the Missouri Orthopedic Institute with access granted only to the designated research personnel. Data will be stored on the Department of Orthopaedic Surgery shared drive and/or Patient IQ, a HIPAA-compliant cloud-based platform that is contracted with the Department of Orthopaedic surgery.

The investigator and research coordinators will monitor the study data. They will review the conduct of clinical studies to assure that the clinical investigators abide by their obligations to conduct clinical studies properly. The investigator will also ensure that the research staff is given access to all study-related documents and study-related facilities, as applicable, and has adequate space to conduct the monitoring, when applicable. The coordinator will review all source documents and compare them to the data contained in the electronic case report forms (eCRF). Staff members will ensure data integrity at three-month intervals during the study.

### ***Adverse Event***

An AE is any untoward medical occurrence in a clinical investigation subject, which changes the medical baseline of the subject. An AE can be an unfavorable and unintended sign, symptom, or disease, whether related to the study device (AEs may also be referred to as complications).

#### ***Anticipated Adverse Event***

An anticipated AE is an AE, of which the nature, severity or degree of incidence is known and identified in applicable product labeling, published literature or the study protocol. The list of anticipated events is provided in section VIII, Potential Risk.

#### ***Serious Adverse Event***

A SAE meets one or more of the following definitions:

- Resulted in in-patient hospitalization
- Resulted in prolonged existing hospitalization
- Resulted in persistent or significant disability/incapacity
- Resulted in permanent impairment of a body function or permanent damage to a body structure
- Necessitated medical or surgical intervention to preclude permanent impairment of a body function or permanent damage to a body structure
- Was a life-threatening situation
- Resulted in participant death

#### ***General Physical Examination Findings***

At screening for inclusion into the study, any clinically significant abnormality should be recorded as a preexisting condition. From the time of consent forward, any new clinically significant findings or abnormalities that meet the definition of a protocol defined AE must also be recorded and documented as an AE.

The PI of the study, [name], and study coordinators will review participant charts and study data (including patient reported outcome measures through Patient IQ) at every clinical follow up visit. During the follow up visit, investigators and coordinators will seek information relating to the participant's health by asking a series of questions and ask as to whether they have seen a doctor for any reason, been hospitalized for any reason or have a current impediment to their function. If any event that is deemed a SAE (listed above) will implement a pause in the participant's study routine until further work up can be obtained.

The adverse event (AE) reporting requirements for this study are as follows:

- All AEs that meet the definition of serious and occur within the period of injection to 90 days following the date of injection.
- All AEs related to the injection site, regardless of seriousness or time of occurrence.

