**Deleted:**

The visits and all research activities are outlined below:

Baseline Visit:

- Consent/Randomization
- Objective Measures:
  - o Serum collection
  - o Urine collection
  - o Synovial fluid collection
  - o General assessments
- Subjective Measures:

- o VAS Pain
- o KOOS-JR
- o UCLA Activity
- Intervention:
  - o Initial injection based on treatment arm

2 Weeks (+/- 6 days) Surveys:

- Subjective Measures:
  - o VAS Pain
  - o KOOS-JR
  - o UCLA Activity

4 Weeks (+/- 1 week) Follow-Up:

- Objective Measures:
  - o Serum collection
  - o Urine collection
  - o Synovial fluid collection
  - o General assessments
- Subjective Measures:
  - o VAS Pain
  - o KOOS-JR
  - o UCLA Activity

8 Weeks (+/- 13 days) Surveys:

- Subjective Measures:
  - o VAS Pain
  - o KOOS-JR
  - o UCLA Activity

12 Weeks (+/- 2 weeks) Surveys:

- Subjective Measures:
  - o VAS Pain
  - o KOOS-JR
  - o UCLA Activity

6 Months (+/- 2 month) Surveys:

- Subjective Measures:
  - o VAS Pain
  - o KOOS-JR
  - o UCLA Activity

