### **VIII. Potential Risks:**

We do not expect any significant medical risks associated with the treatments presented in this study. Most of the risk associated with this study is related to piercing the skin by injection with synovial fluid collection and the venous blood draw. These can include the following: pain, bruising, bleeding, infection, and damage to surrounding structures, such as nerves and blood vessels. The risks of PRP injections include local infection and pain at injection site. The risks of corticosteroid injections include pain at injection site, skin discoloration, elevated blood sugar, infection, cartilage deterioration, and allergic reaction.

Synovial fluid collection in this study is part of the injection process and a stand-alone procedure at the 4-week visit. It has the same risk as the risk for injections listed previously. If there is a concern with the risks associated with the study, the participants are recommended to ask their provider for more information regarding the risks of the injection to their specific health condition. At any point, the participant has the right to withdraw from the study without recourse.

To help lower these possible risks, only professionally trained individuals will participate in the collection of the specimens. The participant will also be monitored for 5-10 minutes after injection.

All adverse events reported spontaneously by the participant or in response to questioning or observation by the investigator/research staff will be assessed for subject safety, acted upon as needed per situation and be recorded. If the events meet the criteria for IRB reporting, they will be reported to the IRB within five days.

Any adverse event associated with the intervention or deviation from the standard protocol will be evaluated related to subject safety and reporting requirements as well as any potential breach of confidentiality.

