## **XI. Costs:**

Most costs to run this study, including the cost of the injections, the equipment to draw blood and collect urine, the containers to store the blood until the tests are run, and the assays run in the laboratory, will be covered by the department. Participants will not incur any of these costs.

The subjects will be financially responsible for all their standard of care treatment. The initial visit is a standard of care, and the participant will be responsible for covering the cost of the visit itself, not the injection procedure or other testing that may occur during the visit. The 4-week visit is not standard of care and will be covered through an internal research fund. Any clinical visit scheduled due to a reoccurrence of knee pain is standard of care and the participant may choose to receive another injection if indicated. The participant is unblinded during this visit and may choose their preference of injection type if indicated. The participant will accrue the cost of the visit and for the injection if the participant chooses to receive the procedure.

All assays and tests will be completed in the laboratory of the same hospital where samples are acquired, so there will be no transportation outside of the hospital.

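### Serious events are to be collected to day 90 and injection-site events at any time, but the last scheduled safety question is at week 4

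*Protocol*

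**What the plan says.** Section XII sets two collection requirements under General Physical Examination Findings. The first is "All AEs that meet the definition of serious and occur within the period of injection to 90 days following the date of injection". The second is "All AEs related to the injection site, regardless of seriousness or time of occurrence". The Adverse Event Reporting subsection repeats both, extends reporting from consent to study completion, and says the resulting rates will be set against the literature and are expected to be similar.

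On how events are found, Section XII has the investigator and coordinators review charts and study data at clinical follow-up visits. It then states: "During the follow up visit, investigators and coordinators will seek information relating to the participant's health by asking a series of questions". The questions concern doctor visits, hospital stays and current limits on function.

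The Section VII visit outline and schedule table show one clinic contact after baseline, "4 Weeks (+/- 1 week) Follow-Up". The others are surveys, for example "12 Weeks (+/- 2 weeks) Surveys", and list only the three patient-reported scores. General assessments are marked at baseline and week 4 only.

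Two other routes exist. Section VIII covers "All adverse events reported spontaneously by the participant or in response to questioning or observation by the investigator/research staff". Section XI says: "Any clinical visit scheduled due to a reoccurrence of knee pain is standard of care".

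On timing, Section VIII says: "If the events meet the criteria for IRB reporting, they will be reported to the IRB within five days". Adverse Event Reporting in Section XII allows up to two weeks, or ten business days, for unanticipated problems.

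**The concern.** The collection windows run well past the last point at which anyone is scheduled to ask. Take a participant admitted to another hospital in month 2 or 3 for a reason unrelated to the knee. In-patient hospitalization meets the protocol's definition of serious and falls inside the 90 days, so it is required data. As written, no scheduled contact would bring it to light.

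Three things are at stake:

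- **Completeness.** Counts of serious and injection-site events may fall short of what Section XII promises.
- **The comparison with published rates.** An under-count lowers the observed rates and could make that comparison look falsely reassuring.
- **Comparability of the arms.** Unscheduled visits are triggered by pain, and under Section XI the participant is unblinded there. If pain recurs at different rates in the two arms, late events could be found at different rates too.

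The IRB deadlines are a separate and smaller matter. They affect when an event is reported, not whether it is found.

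**Working it through.** The protocol states no event rate or expected count, so there is no figure of its own to reproduce. The check sets the visit schedule against the collection windows.

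**Inputs (Section VII schedule, Section XII windows)**

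| Contact | Window | Type | Safety question scheduled |
|---|---|---|---|
| Week 2 | 14 ± 6 = day 8–20 | Survey | No |
| Week 4 | 28 ± 7 = day 21–35 | Clinic | Yes |
| Week 8 | 56 ± 13 = day 43–69 | Survey | No |
| Week 12 | 84 ± 14 = day 70–98 | Survey | No |
| Month 6 | month 4–8 | Survey | No |
| Month 12 | month 10–14 | Survey | No |

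The week 4 questions can look back over the week 2 period, so the gap starts at week 4.

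**Formula.** Days without a scheduled question = end of window − day of last scheduled question. Share = those days ÷ length of window.

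**Serious events, 90-day window**
- Week 4 visit on day 35: 90 − 35 = 55 days; 55/90 = 61%.
- On day 28: 90 − 28 = 62 days; 62/90 = 69%.
- On day 21: 90 − 21 = 69 days; 69/90 = 77%.

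**Injection-site events, taking one year as 365 days**
- On day 35: 365 − 35 = 330 days; 330/365 = 90%.
- On day 28: 365 − 28 = 337 days; 337/365 = 92%.
- On day 21: 365 − 21 = 344 days; 344/365 = 94%.

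**What cannot be computed.** Turning days into missed events needs the timing of events and the fraction that passive routes catch. The protocol gives neither.

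**Would surveys close the gap?** A week 12 form may come back as early as day 70, which leaves 90 − 70 = 20 days open. The month 6 form cannot arrive before month 4 (about 4 × 30 = day 120), so a dated question on it always reaches back over the end of the 90-day window. Scheduled questions after week 4 that cover time up to day 90 rise from 0 as written to 3 (week 8, week 12, month 6).

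**IRB deadlines.** Section VIII gives five days for events meeting IRB criteria. Section XII gives ten business days (about 14 calendar days) for unanticipated problems, which are themselves reported to the IRB. The same event can therefore fall under both.

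**The case against.** The strongest reply is that nothing here is contradictory. Section XII defines which events are reportable and for how long; it does not promise to question every participant up to day 90. A window served partly by spontaneous report is a workable design. Section VIII also covers events found by questioning or observation without limiting that to visits, unscheduled visits would trigger the same chart review, and Section XII has source documents checked against the eCRF and data integrity checked every three months. Shares of calendar days overstate the problem, above all for injection-site events, since the listed risks are mostly procedural and likely to show early. The objectives include no safety endpoint, and about 70 participants are planned. Five days satisfies both IRB limits, because the longer one is only an outer bound.

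Part of this stands. Collection does not stop at week 4, the percentages are not percentages of events, no primary or secondary result changes, and the IRB mismatch is a wording matter.

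The rest does not close the gap. Comparing source documents with the eCRF cannot reveal an event that was never recorded. Section VIII permits questioning but schedules none. Unscheduled visits reach only participants whose knee pain returns. Any further injection taken at such a visit is likewise followed by no scheduled safety question.

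Two practical cautions about the remedy are also fair. Survey answers must be read promptly, because the protocol has a serious event pause the participant's study routine. A month 4–8 form also relies on recall and on the form being returned.

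**Conclusion.** The concern holds as a gap in scheduled ascertainment. The plan promises serious events to day 90 and injection-site events at any time, but schedules its last safety question for day 21 to 35. That leaves 61 to 77% of the serious-event window, and 90 to 94% of a one-year follow-up for injection-site events, to passive or pain-triggered routes.

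This assumes that the questions are asked only at clinic visits, as Section XII says; that the surveys contain only the three listed scores; and that the week 4 visit falls within its window. The number of events that would be missed is unknown. The primary biomarker objective is unaffected, so this is an improvement the sponsor should make rather than a fatal flaw. A statistical analysis plan could not repair it afterwards, because it cannot recover events nobody asked about.

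**What to change.** Add the three existing Section XII questions (doctor seen, hospital stay, current limit on function) and one injection-site item to the week 8, week 12, month 6 and month 12 surveys. Each form should ask about events since the last contact and request the event date, so that the month 6 form can settle the end of the 90-day window. State who reads returned forms and how soon, and how unreturned forms are chased.

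If the sponsor prefers not to do this, the protocol should say that events after week 4 are passively ascertained, and the comparison with published rates should carry that qualification.

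Separately, reconcile Section VIII with the Adverse Event Reporting subsection of Section XII, so that one IRB deadline applies to the events they share.

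The cost is four items on four surveys already being sent (at most 4 × 70 = 280 forms if about 70 participants enroll and all respond), one wording edit, and coordinator time to read forms and follow up positive answers. No new visit or procedure is needed.

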The medication used in the corticosteroid study arm is Triamcinolone Acetonide 40 mg/1 ml. The corticosteroid is to be ordered and regulated through the Investigational Pharmacy. The corticosteroid vials are to be stored in a lock box within the medical supplies room in the principal investigator's clinic. The medical supply room is up to IDS standards. Monthly temperature logs and expiration logs of the medication will be sent to IDS. The injection will consist of Triamcinolone 40 mg/1 mL (Kenalog) combined with 5 mL of 1% lidocaine and will be administered. The injection at the initial visit is the only established Triamcinolone injection within the study protocol. The participant may elect to receive an additional corticosteroid injection after 3 months after the initial injection if it is indicated by pain scores and physician clinical evaluation. This process may be repeated at other 3-month intervals within the study period, which is standard of care and an FDA approved use of the medication to control pain and treat the knee osteoarthritis.

An Investigational New Drug Application (IND) is not necessary for the products utilized in this study. We do not intend to report the investigation to the FDA as a well-controlled study in support of a new indication and with no intent to use it to support any other significant change in the labeling of PRP or triamcinolone. The use of these products does not involve a route of administration, dose, patient population, or other factors that significantly increases the risk associated with the use of the products. This investigation is not intended to promote or commercialize any of the products utilized.

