#### ***Adverse Event Reporting***

All unanticipated problems (UAPs) involving risks to the participants will be reported to the IRB promptly, but no later than two weeks or 10 business days from the time of identification. An UAP is defined as the following:

- Unexpected (in terms of nature, severity, or frequency) given the information provided in research-related documents and the characteristics of the subject population being studied
- Related or possibly related to participation in the research
- Suggests that the research places subjects or others at a greater risk of harm than was previously known or recognized

Any AE or SAE that is expected, as identified in the study documentation, but is occurring at greater frequency or severity, as determined by the principal investigator's assessment, will be reported to the IRB as a UAP. However, adverse events determined to be unrelated to the study will not be submitted to the IRB.

The study period during which AEs must be reported is normally defined as the period from the initiation of any study procedures to the end of the study treatment follow-up. The start of study procedures is the point of consent. Any AEs which fit the protocol defined reportable events must be reported from the time of consent until study completion.

Information on protocol defined AEs should be recorded immediately in the source document and in the appropriate AE module of the eCRF. All clearly related signs, symptoms and abnormal diagnostic procedure results should be recorded in the source document and grouped under one diagnosis, as appropriate. The clinical course of each event should be followed until resolution or until it is determined at the end of the study that the AE will not resolve.

All injection site events occurring at any time as well as all serious adverse events (SAEs) occurring within 90 days post injection will be collected and compared to published data. It is expected that the AE rates reported for the study will be comparable to those reported in the literature for other corticosteroid and PRP injections.

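### The adverse event rules disagree: section VIII records everything, but section XII collects only injection-site events and serious events to 90 days, leaving late non-local harm uncollected.

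*Protocol*

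**What the plan says.** Three places in the protocol set the scope of adverse event data.

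- **Section VIII (Potential Risks)** is the widest. Events that are volunteered, elicited or observed "will be assessed for subject safety, acted upon as needed per situation and be recorded". There is no limit by time, site or seriousness. The same section lists the steroid risks, among them "elevated blood sugar, infection, cartilage deterioration, and allergic reaction".
- **Section XII, General Physical Examination Findings,** gives the study's reporting requirements as two classes: "All AEs that meet the definition of serious and occur within the period of injection to 90 days following the date of injection" and "All AEs related to the injection site, regardless of seriousness or time of occurrence".
- **Section XII, Adverse Event Reporting,** describes a general reporting period running "from the initiation of any study procedures to the end of the study treatment follow-up". It adds that events fitting the protocol-defined reportable list "must be reported from the time of consent until study completion", and directs protocol-defined events to the source document and the eCRF. Its last paragraph returns to the two classes: "All injection site events occurring at any time as well as all serious adverse events (SAEs) occurring within 90 days post injection will be collected". These are to be compared with published data.

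On exposure, section II fixes one triamcinolone injection at the initial visit and allows a further one after 3 months if indicated. It then states: "This process may be repeated at other 3-month intervals within the study period". Section XI also provides for a further injection, of the participant's preferred type, at a visit for recurrent pain.

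**The concern.** A coordinator who learns of a serious event away from the knee at month 5 gets two answers. Section VIII says to record it. The list and closing paragraph of section XII put it outside what is reported and collected. If the narrow list governs the eCRF, the safety dataset will lack most late serious events and some harms that the protocol itself anticipates. Section XII refers to the section VIII list as the anticipated events, so the collection rule leaves out part of the study's own list.

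The stated use of the data is a comparison with the literature, with the expectation that rates will be similar. If the collection rule removes events that published reports count, the study's rates will look low for that reason alone.

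**Working it through.** The plan gives no figure of its own to reproduce here. The check sets the rules side by side and then measures the gap.

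**Step 1. Classify events under each rule.**

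| Event | Section VIII | Two classes in section XII |
|---|---|---|
| Injection-site event, any seriousness, any time | recorded | in |
| Serious, away from the site, injection to day 90 | recorded | in |
| Serious, away from the site, after day 90 | recorded | out, unless an unanticipated problem |
| Raised blood sugar, not serious | recorded | out |
| Systemic allergic reaction, not serious | recorded | out |
| Cartilage deterioration, not serious | recorded | depends on what injection site means |

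Of the six named steroid risks, three are covered (injection-site pain, skin discoloration and infection, taking the last two as local). Two are clearly outside when not serious, and one is arguable: 3 + 2 + 1 = 6. The two named PRP risks, local infection and injection-site pain, are both covered.

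**Step 2. Share of follow-up inside the 90-day window.** Inputs are 90 days (section XII) and a last contact at 12 months, plus or minus 2 months (section VII), with one month taken as 365.25/12 days.

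- 12 months: 90/365 = 24.7% covered; 365 − 90 = 275 days (75.3%) not covered.
- 10 months: 90/304 = 29.6% covered; 214 days not covered.
- 14 months: 90/426 = 21.1% covered; 336 days not covered.

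**Step 3. What that could mean in participants.** The protocol gives no rate for serious events away from the injection site, so the 12-month risk r is an assumption, shown over a range. With a constant hazard h = −ln(1 − r) and about 70 participants (section VI), the expected number whose first such event falls after day 90 is 70 × [exp(−h × 90/365) − exp(−h)].

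- r = 5%: 2.6 of 3.5 expected.
- r = 10%: 5.2 of 7.0.
- r = 20%: 10.25 of 14.0.

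The share outside the window is 73% to 75% throughout, so it hardly depends on the assumed rate.

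**Step 4. Which injection starts the clock.** Three months is 3 × 365.25/12 = 91.3 days. If the date of injection means the first one, the window closes just before the earliest repeat injection under section II, and serious non-local events after a repeat injection are outside it. If it means each injection, someone injected twice at least 90 days apart has up to 180/365 = 49.3% of follow-up covered, against 24.7% for someone injected once. The text does not choose between these readings.

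**Step 5. When events are asked about.** Section XII places the health questions at clinical follow-up visits. The only scheduled one after baseline is at 4 weeks, plus or minus 1 week (days 21 to 35). Every other scheduled contact is a survey made up of VAS, KOOS-JR and UCLA Activity.

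**The case against.** The strongest reply is that recording and reporting are different layers: section VIII records everything and section XII selects what is reported. The consent-to-completion sentence applies only to protocol-defined reportable events, so it need not compete with the two-class list. It still has work to do, because injection-site events have no time limit. The general-period sentence is hedged as what is normally done.

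This stands in part. The consent-to-completion sentence alone does not prove a contradiction. But the layered reading fails at the last paragraph of Adverse Event Reporting, which uses the two classes for what is collected, and at the sentence tying eCRF entry to protocol-defined events. Protocol-defined could be read as the general adverse event definition earlier in section XII, which would widen eCRF entry, but the collection sentence would still be narrow.

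Four stronger inferences are not supported:

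- **All serious events stop counting at day 90.** Serious injection-site events stay reportable at any time, and unanticipated problems go to the IRB with no 90-day limit. That route also takes expected events that occur at greater frequency or severity. It does not fully close the gap, because a raised frequency is hard to see for events that are not collected.
- **The safety comparison is biased in favour of steroid.** No between-arm safety comparison is stated; the comparison is with published data.
- **Three named steroid risks escape.** Two clearly do when not serious; the third depends on an undefined term.
- **Knee replacements would be missed.** Section VII plans tissue collection at arthroplasty, so the study expects to learn of these operations.

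A 90-day window is also a legitimate choice in itself. The fault is that the protocol does not hold to one rule.

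**Conclusion.** The concern holds in this limited form. Section VIII and the collection rule in section XII cannot both be followed for the same dataset. Under the narrow rule, serious events away from the injection site go uncollected for about 75% of the 12-month follow-up (70% to 79% across the visit window), unless they qualify as unanticipated problems. Two named steroid risks are never collected when not serious, and a third is undecided.

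The planned comparison with published rates would then understate late and non-local events. This assumes that the published sources count such events; the protocol does not describe how those sources collected theirs. The size also assumes that the two-class list governs what enters the eCRF. If section VIII were followed instead, the events would be on record, and the remaining fault would be the conflicting instruction.

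The matter should be corrected, but it does not touch the primary biomarker objective.

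**What to change.** Align sections VIII and XII using the protocol's own wider wording:

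1. State that all adverse events are recorded in the eCRF, as section VIII implies, and that serious events are collected from consent to the 12-month contact. Expedited IRB reporting can remain a defined subset.
2. Add an event question to the surveys already scheduled, since the last scheduled clinic visit is at 4 weeks.
3. Define injection site, and say whether the joint and its cartilage are included.
4. State that any 90-day summary is counted from each injection and is drawn from the full event record.

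Tabulation by arm can be left to the statistical analysis plan. The changes concern data collection only and alter no treatment rule. The cost is an amendment to the wording, one more survey item and slightly more event entry for coordinators.
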